A dose of 25mg/day of HT was chosen due to following reasons 1) EFSA approved hydroxytyrosol as a healthy dietary compound up to 15mg/day. There is a previous unpublished study of using hydroxytyrosol 10mg BID in healthy volunteers with class I obesity (communication with PI). With this dose they did not see any changes in LDL oxidation levels and did not have any adverse effect. We used 25mg of hydroxytyrosol as there is demonstrated safety in previous studies and higher than usual healthy dietary compound.

2 Mammographic Density as a Marker of Breast Cancer Risk

Studies have consistently demonstrated a 4-6 fold increase in breast cancer risk for women with increased mammographic density for up to 8 years following measurement [25, 27, 28]. Breast density as assessed qualitatively by BI-RADS category (1= –almost entirely fat, 2 = –scattered fibroglandular densities, 3 = –heterogeneously dense, 4 = –extremely dense). Randomized studies have demonstrated that tamoxifen lowers mammographic breast density up to 4.3% yearly [29]. Given that tamoxifen has been shown to decrease the risk of breast cancer and does decrease breast density, density change may be a useful surrogate endpoint biomarker for the effect of tamoxifen and other chemopreventive agents on breast cancer incidence. A decrease in density of 1% could potentially translate into a nearly 2% lower risk of developing breast cancer [27]. **Effects of HT on Breast Density:** Data from epidemiological studies demonstrated that increase in olive oil intake was associated with decrease in breast densities[30]. A series of 2,000 women who had undergone routine regular mammography and who had detailed information regarding dietary and lifestyle available were evaluated. The authors reported that women in the highest tertile of olive oil consumption (>30.5 g/day) were associated with 30% reduction in breast density[30].

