2.2 Risk Assessment

- Breast Risk Calculation using the modified Gail risk score [32, 33]. This model is an interactive tool designed to estimate a woman's risk of developing invasive breast cancer in her lifetime and the next 5 years.
 - <http://www.cancer.gov/bcrisktool/>
 - This model can only be used if there is no known diagnosis of DCIS or LCIS
- A patient with a diagnosis of lobular carcinoma in situ (LCIS) or atypical lobular or atypical ductal hyperplasia. Germline mutations of BRCA 1 or BRCA 2 genes. Germline mutations in the PTEN (cowden syndrome) and TP53(Li-Fraumeni syndrome)
- History of unilateral breast cancer 5 years ago
- At least 10% probability of carrying BRCA mutation

3 Objectives and endpoints

Primary

- To conduct a pilot breast cancer prevention study of hydroxytyrosol in women at increased risk of breast cancer.
- To assess whether mammographic density is reduced in pre or post menopausal women at high risk of breast cancer taking hydroxytyrosol for 1 year compared with baseline.

Secondary

- To assess the toxicity of hydroxytyrosol
- To evaluate FACT ES score baseline, 6 months and 1 year.
-

Exploratory objectives (Mandatory biopsy)

[figure not shown]
- To assess whether proliferation (Ki67 staining, Cdkn2a tumor suppressor, cyclin D1), is reduced in women at high risk of breast cancer after taking hydroxytyrosol for 1 year compared with baseline.
- To explore the difference in the expression of other biomarkers of apoptosis (Fas receptor, cleaved caspase-3, caspase-8, cytochrome c), enzymes related to oxidative stress (Fas receptor, cleaved caspase-3, caspase-8, cytochrome c), DNA damage by immunohistochemistry, Wnt signaling(LRP6, β -catenin, Sfrp proteins 1 to 5, DKK1, c-jun, c-myc) and stem cell pathway before and after drug therapy.
- To collect and bank breast tissue from women at high risk of breast cancer prior to and after treatment with hydroxytyrosol for future biomarker analysis.

Exploratory endpoint (MRI Breast Imaging)

- To assess breast MRI density pretreatment and 12 months post hydroxytyrosol therapy in subjects with available breast MRIs.

4 Study design

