4.1 Description of study design

A PILOT STUDY OF HYDROXYTYROSOL, A COMPONENT OF OLIVE OIL FOR BREAST CANCER PREVENTION IN WOMEN AT HIGH RISK OF BREAST CANCER

One hundred (100) pre and post-menopausal women at high risk of breast cancer who have declined tamoxifen, raloxifene or aromatase inhibitor (standard of care) will receive 25mg HT. Eligible women will have a 5 yr risk by Gail Model ≥ 1.7 , or 10% probability of BRCA mutation by BRCAPRO or similar model, or have a previous breast biopsy showing LCIS, atypical lobular or ductal hyperplasia, or have a known germline mutation in *BRCA1* or *BRCA2*. Patients with unilateral breast cancer 5 or more years prior to registration are also allowed. The main exclusion criteria include women who are pregnant or breast feeding, with diagnosis of any malignant disease, or with inability to take oral medication. The women will undergo a mammogram as well as a biopsy of normal breast tissue before and after taking study drug. This biopsy will be directed to the upper outer quadrant, which is typically a dense region. The primary endpoint of this study is change in mammographic density after treatment with HT. The Secondary endpoint will assess toxicity, apoptosis (Fas receptor, cleaved caspase-3, caspase-8, cytochrome c) and cell proliferation (Ki 67 staining, Cdkn2a tumor suppressor, cyclin D1), enzymes related to oxidative stress (ROS and related enzymes), DNA damage by immunohistochemistry, stem cell markers (CD44, CD24, and ALDH), and affection of Wnt signaling (LRP6, β -catenin, Sfrp proteins 1 to 5, DKK1, c-jun, c-myc) before and after drug therapy. If patients undergo a breast MRI before and/or after the completion of the drug, the images will be collected. The study drug will be supplied by PLThomas & Co.. The patients will have a study visit at 3, 6 and 12 months. The study visit will include a general history and physical exam, an assessment for safety and concomitant medications and pill

count. After completion of therapy, the patient will undergo a mammogram as well as a second breast biopsy.

5 Study Population

Each of the criteria in the following section must be met in order for a participant to be considered eligible for registration.

Study Duration:

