reported as a follow-up to that event regardless of when it occurs. The follow-up information should describe whether the event has resolved or continues, if and how it was treated, whether the blind was broken or not (if applicable), and whether the patient continued or withdrew from study participation.

If the SAE is not previously documented in the Hydroxytyrosol Investigator Brochure or Package Insert (new occurrence) and is thought to be related to the study drug, may urgently require further information from the investigator for Health Authority reporting. TMHCC and TMHRI may need to issue an Investigator Notification (IN), to inform all investigators involved in any study with the same drug that this SAE has been reported. Suspected Unexpected Serious Adverse Reactions (SUSARs) will be collected and reported to the competent authorities and relevant ethics committees in accordance with Directive 2001/20/EC or as per national regulatory requirements in participating countries.

For Comparator Drugs/Secondary Suspects (Concomitant Medications), all serious adverse experiences will be forwarded to the comparator drug company by the investigator.

9 Statistical methods

Study Design and Sample Size. This is a single-arm, pilot breast cancer prevention study of hydroxytyrosol in women at increased risk of breast cancer. Our primary study endpoint will be defined as proportion of women who exhibit a 10% absolute reduction in mammographic density at one-year of follow-up (Cuzick JNCI 2011). For each of the post and pre-menopausal group of women, we will assume under the null hypothesis that 25% of women will exhibit a response (at least a 25% reduction from baseline) versus an alternative hypothesis equal to 45% based on data presented from Cuzick (JNCI 2011). Under these assumptions, a sample of 50 pre-menopausal and 50 post-menopausal women will provide 85% power based on a two-sided test for a single proportion with 5% significance level for each group of women.

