Statistical Analysis. Demographics and pre-treatment characteristics will be summarized for 50 premenopausal & 50 postmenopausal women using descriptive statistics. Mammographic density levels at baseline and follow-up time-points as well as categorized levels based on BIRAD criteria will also be summarized using means, standard deviations and proportions. Change from baseline levels of breast density will be analyzed using paired tests while the proportion of women who exhibit at least a 10% absolute reduction from baseline will be calculated along with 95% binomial confidence intervals for each group of women.

Correlative endpoints including Ki-67, apoptosis, Wnt signaling and stem cell pathway markers will likewise be summarized descriptively at each time point of follow-up. Correlations between these markers and with mammographic density levels will be assessed using Spearman or Pearson's correlation coefficients. Change from baseline levels will be analyzed using paired t-test or Wilcoxon-signed rank test.

Multivariate analysis to adjust for demographic/clinical characteristics, specifically age or menopausal status (pre, peri, and post) will likewise be considered using logistic regression for analyzing proportion of women with response or using linear regression models for analysis of quantitative levels of mammographic density. Given the pilot nature of this study, these multivariate analyses will be considered exploratory.

Expected outcome: We expect a decrease in apoptosis, cell proliferation, in post-treatment breast tissue in comparison to pre-treatment. Our previous data reveal an inhibition of Wnt signaling by HT, thus we expect a change in this signaling in this prevention study.

Potential pitfalls, and resolutions: If we do not have enough breast tissue for all determinations, it will be difficult to measure mRNA levels. In such a scenario, we can determine the expression of Sfrp proteins only by multiplex nucleic acid *in situ* hybridization technology (RNAscope) in paraffin embedded tissue slides.

CONFIDENTIAL

10 References:

1. Siegel, R., D. Naishadham, and A. Jemal, Cancer statistics, 2012. *CA Cancer J Clin.* 62(1): p. 10-29.
2. Anderson, D.E., Genetic study of breast cancer: identification of a high risk group. *Cancer*, 1974. 34(4): p. 1090-7.
3. Jatoi, I. and A.B. Miller, Why is breast-cancer mortality declining? *Lancet Oncol.* 2003. 4(4): p. 251-4.

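### Sections 3 and 4.1 describe the primary endpoint as change in density, Section 9 defines it as a responder proportion, and an unranked paired test leaves open which result decides the trial

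*Combined protocol and SAP*

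**What the plan says.** Four places bear on the primary endpoint.

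- **Section 3 (primary objectives):** "To assess whether mammographic density is reduced in pre or post menopausal women at high risk of breast cancer", taking hydroxytyrosol for one year and compared with baseline. No threshold is given.
- **Section 4.1:** "The primary endpoint of this study is change in mammographic density after treatment with HT". Again there is no threshold or responder rule.
- **Section 9, design and sample size:** "Our primary study endpoint will be defined as proportion of women who exhibit a 10% absolute reduction in mammographic density at one-year of follow-up". For each menopausal group, "we will assume under the null hypothesis that 25% of women will exhibit a response", against an alternative of 45%. Groups of 50 are said to give 85% power with a two-sided 5% test of a single proportion. The parenthesis that explains response in this paragraph reads "at least a 25% reduction from baseline", which is not the same rule as a 10% absolute reduction.
- **Section 9, statistical analysis:** "Change from baseline levels of breast density will be analyzed using paired tests". The same sentence adds the proportion with at least a 10% absolute reduction, with a 95% binomial confidence interval per group. Neither analysis is called primary or secondary here, and the 25% null is not repeated.

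Section 2 gives the only benchmark for the size of a drug effect on density: "Randomized studies have demonstrated that tamoxifen lowers mammographic breast density up to 4.3% yearly".

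**The concern.** Whether density has fallen from baseline is a different question from whether more than a quarter of women have fallen by 10 points. The natural test of the first is the paired test in Section 9, whose null is no change. The second is the test for which the trial was sized.

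A reader of Sections 3 and 4.1 could take a significant paired result as meeting the primary objective. A reader of the sample size paragraph could not. No passage says what follows if the two results differ. In a single-arm study with no control group, a hurdle fixed in advance is the main protection against over-claiming. If a success claim can rest on either result, that protection weakens, and the planned power does not apply to a claim based on the paired test.

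**Working it through.** **1. The plan's own figure.** Inputs from Section 9: n=50 per group, 25% against 45%, two-sided alpha 5%. By the arcsine approximation the effect size is 2·arcsin(√0.45) − 2·arcsin(√0.25) = 1.4706 − 1.0472 = 0.4234. Then 0.4234 × √50 = 2.994, and power = Φ(2.994 − 1.960) = 84.9%. The stated 85% reproduces, for the responder proportion only.

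**2. The cutoff that the test implies.** Section 9 does not name the exact test, and the choice moves the cutoff by one woman.

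| Responders | Exact two-sided p against 25% | Clopper-Pearson lower limit | Wilson lower limit | Power at 45% |
|---|---|---|---|---|
| 19/50 | 0.048 | 24.7% | 25.9% | 87.3% |
| 20/50 | 0.021 | 26.4% | 27.6% | 80.3% |

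Both cutoffs are carried forward.

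**3. Can the two analyses disagree on the same data?** Two constructed data sets of 50 women answer this without assuming a standard deviation. The paired statistic is t = mean change / (SD/√50) on 49 degrees of freedom.

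- *Paired test positive, responders not.* Twelve women change by −12 points and 38 are spread evenly from −8 to +4. The mean change is (12 × −12 + 38 × −2)/50 = −4.4 and the SD is 5.33, so t = −4.4/(5.33/√50) = −5.84 and p = 4×10⁻⁷. Responders are 12/50 = 24%, with exact p = 1.0 against 25%.
- *Responders positive, paired test not.* Twenty women change by −12 and 30 by +7. The mean change is (20 × −12 + 30 × 7)/50 = −0.6 and the SD is 9.40, so t = −0.45 and p = 0.65 (Wilcoxon p = 0.08). Responders are 20/50 = 40%, with exact p = 0.021.

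**4. How often might they disagree? Illustration only.** Assumptions: changes are normal; the true mean fall is 4.3 points, which reads the tamoxifen figure in Section 2 as percentage points over one year; the SDs are chosen to span a range, because the documents give none. The responder rate is 1 − Φ((10 − 4.3)/SD). Paired power comes from the noncentral t distribution with noncentrality 4.3/(SD/√50). Responder success is the exact binomial tail with n=50.

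| SD (points) | Responder rate | Paired test succeeds | 19 or more of 50 | 20 or more of 50 |
|---|---|---|---|---|
| 8 | 23.8% | 96% | 1.8% | 0.8% |
| 10 | 28.4% | 85% | 9% | 5% |
| 12 | 31.7% | 70% | 21% | 14% |
| 15 | 35.2% | 51% | 39% | 28% |
| 18 | 37.6% | 38% | 53% | 41% |

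The paired test succeeds far more often at small SDs. The gap closes as the SD grows, and by SD 18 the order has reversed under either cutoff.

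**5. The two responder rules in Section 9.** If the 25% reduction is relative to baseline, it equals 10 points only where 0.25 × baseline = 10, that is, at a baseline density of 40%. At a baseline of 20% it is 5 points; at 60% it is 15 points.

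**The case against.** The strongest reply is that the sections form an ordinary sequence: Section 3 states an objective, Section 4.1 names the variable, and Section 9 gives the operational definition. Sections 3 and 4.1 mention no mean, no null of zero and no test; linking them to the paired test is an inference. Within Section 9 only the responder proportion is called primary, and only it has hypotheses, alpha, power and a sample size. This largely stands. A reader might infer that the plan sets up two primary endpoints of equal standing, and the documents do not support that. What remains is that Section 4.1 calls change itself the primary endpoint, and that the analysis paragraph plans a test that answers the Section 3 question directly without ranking it.

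A reader might also infer that a tamoxifen-sized fall would nearly always pass the paired test and fail the responder test. That holds only for small SDs, and no SD is given. The 4.3% is an upper figure with its units unstated. Normality is also doubtful: density is bounded at 0 to 100% (Section 2.1), and women just above 10% density are eligible (Section 5.1), so some can barely fall by 10 points.

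Nor does the comparison with tamoxifen show that the 45% alternative is unrealistic. That is a separate question, and Section 9 rests the rate on a cited study that is not among the documents.

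The study is a pilot, but Section 9 reserves the exploratory label for the multivariate analyses and sets a formal test with stated power in each group.

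**Conclusion.** The point holds as an inconsistency in how the primary endpoint is described, together with a missing rank for the paired test. Section 9 makes the responder proportion the better-supported reading, but Sections 3 and 4.1 leave room to claim success on the paired change. The two constructed data sets show that the results can conflict in either direction at n=50, and they need no assumed SD. The probabilities in the illustration rest on normality, on reading 4.3% as points and on assumed SDs; they show that disagreement can be frequent, not that it will be. The power statement is arithmetically sound for the responder proportion. That endpoint cannot yet serve as sole primary, because Section 9 gives two responder rules and does not make clear to which of them the 25% and 45% rates belong. The matter should be settled before analysis.

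**What to change.** 1. In Sections 3, 4.1 and 9, name the responder proportion against 25%, per menopausal group, as the sole primary endpoint.
2. Use one responder definition throughout. Reconcile the 10% absolute reduction with the 25% reduction from baseline in Section 9, and confirm that the 25% and 45% rates refer to the definition kept.
3. In the analysis paragraph, state the test against 25% and the resulting cutoff (19 or 20 of 50, depending on the method).
4. Label the paired analysis of mean change in Cumulus percent density, with its 95% confidence interval, as secondary, and state that it is not sufficient to meet the primary.

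This needs wording changes only, with no new data, visits or participants; if the 25% and 45% rates prove to belong to the other definition, the sample size statement needs a fresh justification. The downside is real: a significant paired change alone can no longer be reported as a positive primary. A modest mean fall, including one the size of the tamoxifen benchmark, may be reported as not meeting the primary; the fix makes that outcome explicit and does not prevent it.

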The duration of patient participation in the study treatment will be a total of 12 months, which is counted from the start of treatment. Study Follow-up for all patients will include medical history update (30 days after the last dose of the study drug)

Safety Criteria:

All participants will be assessed by a physician for pre-existing medical conditions and baseline physical abnormalities prior to the initiation of investigational therapy. Patients presenting with any medical history, physical exam, or laboratory abnormality that, in the opinion of the treating physician, would put the subject's safety at risk will be excluded. Baseline signs and symptoms are to be recorded and followed throughout the trial. These will be monitored throughout the study and recorded if they increase in severity or frequency during treatment or within the follow up period. Participants will be assessed for adverse events by a physician or designated midlevel provider while the subject is on study. Vital signs including blood pressure, heart rate and temperature should be performed at each physical exam. Assessments may be performed more frequently if clinically indicated. In addition, hematology and serum chemistry profiles will be drawn prior to the initiation of treatment to determine whether the study drug combination affects hematologic values, electrolytes or liver function tests. Laboratory assessments will be performed more frequently if clinically indicated. This clinical and laboratory data will be used to determine whether these women in the study with Hydroxytyrosol have any symptoms or side effects associated with the study medications. Subjects will be followed for adverse events for a period of 30 days after the completion of investigational therapy. Patients with abnormal laboratory or clinical findings that are believed to be treatment related will be followed until the condition resolves or stabilizes, or until the laboratory values are no longer considered clinically significant.

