6.2.2.3 Compliance

The investigator/designee will count remaining unused hydroxytyrosol at each visit to assess compliance. A study medication log is provided in the CRF to capture subject compliance. If the subject forgets to return unused hydroxytyrosol at a scheduled visit, compliance will be confirmed by direct questioning of the subject. Subjects should be instructed to record any missed doses of hydroxytyrosol.

Compliance with hydroxytyrosol will be calculated by the ratio of number of pills actually taken to the number of pills that should have been taken. Compliance will be defined as a ratio ≥ 0.75 . Subjects with ratios between 1.00 and 0.75 will be allowed to continue on study. The importance of compliance with study medication should be reinforced to subjects with a ratio of less than 1.00. Subjects who have ratios < 0.75 will be taken off study for non-compliance.

Compliance with hydroxytyrosol will be evaluated by a physical pill count. In the event that the patient forgets to bring unused drug/empty drug bottles to the study visit, patients will be queried by study staff regarding compliance.

6.2.2.4 Post Intervention Follow Up Phone Call (Month 13; Day 390 +/- 7 days):

Participants will be called for assessment and/or resolution of adverse events.

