7.1 Study flow and visit schedule

Table 7-1 Visit evaluation schedule

Required Studies	Prestudy Evaluation	Day 1	Month 1-2 (Day 30 to 60)	Month 3 (day 90) ¹	Month 6 (day 180) ¹	Month 9 (day 270) ¹	Month 12 (day 360) ¹	Month 13 (day 390) ¹
Clinic Visit								
Breast Cancer Risk Assessment ²	X							
Baseline and Pre-existing conditions	X							
History and Physical Exam ¹³	X			X	X		X	
Height and Weight	X						X	
Vital Signs	X			X	X		X	
Performance Status	X						X	
Toxicity Notation ³				X	X		X	X ¹²
Review of Intake Calendar ⁴				X	X		X	
Laboratory								
Serum liver function tests	X			X	X		X	
Serum lipid panel (fasting)	X			X	X		X	
PT/PTT/INR ⁵	X						X	
FSH (if necessary) ⁶								
CBC and CMP	X			X	X		X	
Serum Pregnancy ¹⁴	X							
Radiographs								
Bilateral Mammogram ⁷	X						X	
Bilateral Breast MRI image collection ⁷	X						X	
Bone Density ⁸	X						X ⁸	
Procedures								

Random core biopsy ⁹	X						X	
Intervention								
Dispense study drug ¹⁰		X			X			
Count Pills				X	X		X	
Questionnaire ¹¹	X				X		X	

1. Followup visits can occur (+/- 14 days for each assessment) to allow flexibility in scheduling. Follow-up visits will continue even if the participant goes off study intervention early unless there is a withdrawal of consent.
2. Risk assessment using Gail risk model if no known history of DCIS or LCIS and no deleterious mutation in BRCA 1 or 2, PTEN or P53
3. On months 3, 6, 12 (Days 90, 180, 360 (+/- 14 days for each assessment)) adverse events will be noted
4. On months 3, 6, and 12 (90, 180, 360 +/- 14 days for each assessment), participants will be seen at the study sites to review the intake calendar which will document drug compliance and date of last menses.
5. PT/PTT/INR required if the patient has been on anticoagulation therapy within 7 days prior to breast core biopsy.
6. FSH only to be performed if menopausal status needs to be determined (e.g. in patient with hysterectomy with at least one ovary intact – see section 7.2.2)
7. Mammogram within 90 days of registration. Imaging to be done prior to breast biopsy. Bilateral Breast MRI images to be collected if conducted within 90 days of registration at baseline End of treatment Breast MRI images to be collected if available.
8. This test information will be collected if available. Bone density not to be ordered specifically for the study..

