8.1 Adverse events

8.1.1 Definitions and reporting

Adverse events that begin or worsen after informed consent should be recorded in the Adverse Events CRF. Conditions that were already present at the time of informed consent should be recorded in the Medical History page of the patient's CRF. Adverse event monitoring should be continued for at least 30 days (or 5 half-lives, whichever is longer) following the last dose of study treatment. Adverse events

(including lab abnormalities that constitute AEs) should be described using a diagnosis whenever possible, rather than individual underlying signs and symptoms. When a clear diagnosis cannot be identified, each sign or symptom should be reported as a separate Adverse Event.

The occurrence of adverse events should be sought by non-directive questioning of the patient at each visit during the study. Adverse events also may be detected when they are volunteered by the patient during or between visits or through physical examination, laboratory test, or other assessments. As far as possible, each adverse event should be evaluated to determine:

1. The severity grade (CTCAE Grade 1-4)
2. Its duration (Start and end dates or if continuing at the Safety Follow-up Visit)
3. Its relationship to the study treatment (Reasonable possibility that AE is related: No, Yes)
4. Action taken with respect to study or investigational treatment (none, dose adjusted, temporarily interrupted, permanently discontinued, hospitalized, unknown, not applicable)
5. Whether medication or therapy was given (no concomitant medication/non-drug therapy, concomitant medication/non-drug therapy)
6. Outcome (not recovered/not resolved, recovered/resolved, recovering/resolving, recovered/resolved with sequelae, fatal, unknown)
7. Whether it is serious, where a serious adverse event (SAE) is defined as in Section 8.2.1

All adverse events should be treated appropriately. Such treatment may include changes in study drug treatment including possible interruption or discontinuation, starting or stopping concomitant treatments, changes in the frequency or nature of assessments, hospitalization, or any other medically required intervention. Once an adverse event is detected, it should be followed until its resolution, and assessment should be made at each visit (or more frequently, if necessary) of any changes in severity, the suspected relationship to the study drug, the interventions required to treat it, and the outcome.

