Information about common side effects already known about the investigational drug can be found in the [\[Investigators' Brochure\]](#). This information should be included in the patient informed consent and should be discussed with the patient during the study as needed.

Adverse event monitoring should be continued for at least 30 days following the last dose of study treatment

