8.2.2 Reporting

The principal investigator has the obligation to report all serious adverse events to the FDA, and institutional IRB.

All events reported to the FDA by the investigator are to be filed utilizing the Form FDA 3500A (MedWatch Form).

To ensure patient safety, every SAE, regardless of suspected causality, occurring

- after the patient has provided informed consent and until at least 30 days after the patient has stopped study treatment/participation
- after protocol-specified procedures begin (e.g., placebo run-in, washout period, double-blind treatment, etc.) and 30 days after the patient has stopped study treatment
- after the start of any period in which the study protocol interferes with the standard medical treatment given to a patient (e.g., treatment withdrawal during washout period, change in treatment to a fixed dose of concomitant medication) and until 30 days after the patient has stopped study treatment

must be reported to The Methodist hospital research Institute and The Methodist hospital Cancer Center within 24 hours of learning of its occurrence (**[contact]**). This includes serious, related, labeled (expected) and serious, related, unlabeled (unexpected) adverse experiences. All deaths during treatment or within 30 days following completion of active protocol therapy must be reported within 5 working days.

Any SAEs experienced after this 30 days period should only be reported to TMHS and TMHCC if the investigator suspects a causal relationship to the study drug. Recurrent episodes, complications, or progression of the initial SAE must be reported as follow-up to the original episode within 24 hours of the investigator receiving the follow-up information. A SAE occurring at a different time interval or otherwise considered completely unrelated to a previously reported one should be reported separately as a new event. The end date of the first event must be provided.

The original copy of the SAE Report and the fax confirmation sheet must be kept within the Trial Master File at the study site.

Follow-up information is sent to the same fax number as the original SAE Report Form was sent, using a new fax cover sheet, stating that this is a follow-up to the previously reported SAE, and giving the date of the original report. Each re-occurrence, complication, or progression of the original event should be

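### Adverse-event follow-up must run at least 30 days after the last dose, but the Month 13 call and the end-of-follow-up rule use other clocks and windows that do not secure it

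*Combined protocol and SAP*

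**What the plan says.** The safety requirement is tied to the last dose:

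- Section 5 (Safety Criteria): "Subjects will be followed for adverse events for a period of 30 days after the completion of investigational therapy".
- Section 5 (Study Duration): "Study Follow-up for all patients will include medical history update (30 days after the last dose of the study drug").
- Section 8.1.1: "Adverse event monitoring should be continued for at least 30 days (or 5 half-lives, whichever is longer"), and again at the end of that section: "Adverse event monitoring should be continued for at least 30 days following the last dose of study treatment".
- Section 8.2.2, for serious events: "until at least 30 days after the patient has stopped study treatment/participation".

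The schedule is tied to other dates:

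- Section 6.2.2.1 counts follow-up assessments from treatment start. Treatment lasts 12 months, also from that date, and Section 6.2.2.2 and Table 7-1 equate Month 12 with Day 360.
- After Month 12, the only toxicity entry in Table 7-1 is the Month 13 telephone call. Section 6.2.2.4 is headed "Post Intervention Follow Up Phone Call (Month 13; Day 390 +/- 7 days").
- Section 7.2 lists Day 390 among the adverse-event assessments with a tolerance of 14 days. Footnote 1 of Table 7-1, which is attached to the Month 13 column, agrees: "Followup visits can occur (+/- 14 days for each assessment) to allow flexibility in scheduling".
- Section 6.2.2.8, item 8, ends required follow-up 13 months after registration.

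The second biopsy stands in the Month 12 column of Table 7-1, but Section 6.2.2.2 allows it during the four weeks after the drug is stopped.

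**The concern.** A minimum measured from the last dose is being delivered by a call measured from treatment start, under two different tolerances, with a closing rule measured from registration. Site staff work from the visit table. They could meet every date in it and still make the last safety contact before the 30 days that the text requires.

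Toxicity is a secondary objective (Section 3), and Section 8.1.1 relies on questioning at each visit to find events. An early last contact leaves the tail of the period to whatever the woman volunteers. If the biopsy is done late and the call early, nobody is scheduled to ask about hematoma or infection, both of which Section 6.2.2.5 lists as possible complications.

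**Working it through.** All days are counted from treatment start.

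**Inputs.** Last dose Day 360 (Month 12 in Section 6.2.2.2 and Table 7-1). Call at Day 390, plus or minus 7 (Section 6.2.2.4) or 14 (Section 7.2; Table 7-1, footnote 1). Biopsy up to 28 days after stopping (Section 6.2.2.2), or in the Month 12 column, Day 360 plus or minus 14. Follow-up ends 13 months after registration (Section 6.2.2.8, item 8).

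The supply is consistent with a Day 360 last dose. Bottles hold 90 capsules (Section 6.1). If a six-month supply is two bottles (an assumption), two dispensings give 2 x 2 x 90 = 360 daily capsules, the last on Day 360 if none is missed.

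**Step 1. The plan's own figure.** 390 - 360 = 30 days. The nominal schedule reproduces the requirement exactly, with no margin.

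**Step 2. The two windows.** Gap = day of call - 360.

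| Window | Permitted call days | Gap after last dose | Permitted days with gap under 30 |
|---|---|---|---|
| +/- 7 | 383 to 397 | 23 to 37 | 383 to 389: 7 of 15 |
| +/- 14 | 376 to 404 | 16 to 44 | 376 to 389: 14 of 29 |

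The last column counts permitted days. It is not a probability that a call will be early.

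**Step 3. The end-of-follow-up rule.** Thirteen months is 13 x 365/12, about 395 days. Let g be the days from registration to first dose. Required follow-up then ends on Day 395 - g, which is 395 - g - 360 = 35 - g days after the last dose. This is under 30 once g exceeds 5, and from that point it also ends before the nominal Day 390 call. The plan does not state g. Over an assumed range of 0 to 30 days:

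| g | Follow-up ends | Days after last dose |
|---|---|---|
| 0 | Day 395 | 35 |
| 5 | Day 390 | 30 |
| 14 | Day 381 | 21 |
| 30 | Day 365 | 5 |

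The upper end borrows the 30 days from consent that Section 6.2.2 allows for the baseline biopsy; it is only a guide, since that clock starts at consent. If 13 months is read as 390 days, the plan's own convention for Month 13, each figure in the last column falls by 5 and any gap at all gives under 30 days.

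**Step 4. The biopsy.** Under the four-week allowance the latest date is 360 + 28 = Day 388. The earliest call precedes it by 388 - 383 = 5 days (+/- 7) or 388 - 376 = 12 days (+/- 14). A call on Day 390 follows it by 2 days. Under the Month 12 column the latest date is 360 + 14 = Day 374, before the earliest call under either window.

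**The case against.** The strongest reply is that the 30-day duty is written out several times and a scheduling tolerance does not cancel an express minimum. For a Day 360 last dose, staff can satisfy both by calling on Day 390 to 397, which lies inside both windows. Capture also does not depend on the call alone. Section 8.1.1 accepts events volunteered between visits and follows each to resolution, and Section 8.2.2 requires serious events to be reported for at least 30 days whatever the date of the call. The windows can also run in the patient's favour: a woman whose last dose is at a Day 346 completion visit has at least 383 - 346 = 37 days (+/- 7) or 376 - 346 = 30 days (+/- 14).

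Most of this stands, and it limits the size of the problem. It does not remove it. No text ranks the 30-day duty above Table 7-1, the two tolerances cannot both be right, and item 8 expressly releases the site from follow-up on a date that may come before the 30 days are complete.

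Four stronger inferences are tempting, and the documents do not support them:

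- *That women who stop early lose their 30 days.* Sections 6.2.2.9 and 7.2 keep them on the schedule, so the 30 days fall inside continuing follow-up. Questioning may be delayed, but follow-up is not missing.
- *That the biopsy is left without a later safety contact.* This needs the four-week allowance and an early call together. On the Table 7-1 timing it cannot happen.
- *That the medical history update is missing.* It has no row of its own, but the Month 13 call can serve as the update.
- *That much shorter gaps are typical.* Taking 12 months as 365 days makes the nominal gap 390 - 365 = 25 days, and dosing to a Day 374 visit makes the shortest +/- 7 gap 383 - 374 = 9 days. But the plan equates Month 12 with Day 360, and on the supply assumption above, dosing past Day 360 needs missed doses or extra capsules.

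**Conclusion.** The point holds as an internal conflict in the current text. With a last dose on Day 360, the schedule permits closing safety contact at 23 days under one stated window and 16 under the other, against a required minimum of 30. The end-of-follow-up rule falls short once registration precedes the first dose by more than about 5 days; that part rests on a gap the plan does not give. A reader might infer that the schedule forces inadequate follow-up. It does not: the nominal days give exactly 30, and a compliant date is available for a Day 360 last dose.

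The practical effect is small. Section 1.2.1.3 reports that a single dose was undetectable in plasma within 2 hours, so late drug toxicity is unlikely, and the primary endpoint is untouched. What is gained is one consistent rule and a complete 30-day record, together with a safety question after the biopsy when it is done late.

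**What to change.** 1. In Sections 6.2.2.4 and 7.2 and the Month 13 column of Table 7-1, exempt Month 13 from footnote 1 and state one rule: *The final adverse-event call, which also serves as the medical history update, is made 30 to 37 days after the last dose; if the second biopsy has not been done by then, the call is made after the biopsy. For women who stop early, the final call is made on Day 390 to 397, after the one-year biopsy.*
2. Replace item 8 of Section 6.2.2.8 with: *All participants will be followed until the final adverse-event call in Section 6.2.2.4; unresolved treatment-related events are followed per Sections 5 and 8.1.*

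Check: a last dose on Day 360 gives a call on Day 390 to 397. A biopsy on the last allowed day (28 days after stopping) is followed by the call 30 - 28 = 2 to 37 - 28 = 9 days later. Any last dose before Day 360 leaves more than 30 days before a Day 390 call, so the rule for early stoppers meets the minimum wherever the line between stopping early and completing is drawn up to that day.

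The cost is wording in four places, with no added visit or test. The last call moves a few days later for some women. An extra call 30 days after an early stop would shorten recall, but it is optional and not needed to correct the error.
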